Study on the relationship between plasma MRD and cfDNA
HPV and the efficacy and prognosis of locally advanced
cervical cancer after concurrent chemoradiotherapy

Project Title: Relationship between plasma MRD and cfDNA HPV and efficacy
and prognosis after concurrent chemoradiotherapy for
locally advanced cervical cancer

Project leader/principal investigator: [name]

Department: Department of Oncology, Guizhou Provincial People's Hospital

Project undertaking unit: Guizhou Provincial People's Hospital

Project chair: Guizhou Provincial People's Hospital

Project Year: 2024/01 – 2026/12

Version number: V1.0

Version date: 2023-05-22

A. 、 Purpose of the study

1. Main objective: To detect the expression levels of MRD and plasma HPV before and after concurrent chemoradiotherapy for cervical cancer based on cfDNA liquid biopsy, and to evaluate the efficacy and recurrence risk of cervical cancer after concurrent chemoradiotherapy by the expression levels of MRD and plasma HPV
2. Secondary objectives: To facilitate clinical decision-making on whether to adjuvant chemotherapy, as well as the timing of adjuvant chemotherapy and the benefits of adjuvant chemotherapy through the expression levels of MRD and plasma HPV.

B. 、 Types of study design, principles and procedures

1. study design

This is a prospective, observational, single-center study

2. Study population and sample size considerations

Study population: Cervical cancer patients diagnosed with initial visit to Guizhou Provincial People's Hospital from November 2022 to November 2024 were collected.

Sample content estimation

There were about 30 cases in the experimental group, and the sample estimation was estimated by Power and Sample Size Program software, α 0.05, Power 0.8, δ and σ were obtained according to the literature review, m was 0.5.

2.1 Inclusion Criteria:

- (1) Age: ≥ 18 years old, ≤ 75 years old.
- (2) Pathological histologic confirmation of cervical cancer.
- (3) Imaging or PET/CT examination can be performed to understand the tumor

and complete all follow-up.

- (4) Measurable lesions before treatment.
- (5) Good physical condition: ECOG score 0-1 (or KPS score 70-100).
- (6) Estimated survival ≥ 6 months.
- (7) The baseline blood routine and biochemical indexes before radiotherapy and chemotherapy met the following standards: hemoglobin ≥ 80 g/L, absolute neutrophil count (ANC) $\geq 1.5 \times 10^9$ /L, platelet $\geq 100 \times 10^9$ /L, ALT, AST \leq 2.5 times the normal upper limit; Serum albumin ≥ 30 g/L.
- (8) There are three preoperative items: if the patient has syphilis, plum repellent therapy is required before treatment.
- (9) The patient has no history of allergy to rubber products.
- (10) Cardiopulmonary function is basically normal

2.2 Exclusion criteria:

- (1) Those who are allergic to rubber products.
- (2) Those with severe acute infection and uncontrolled or purulent and chronic infection wounds that do not heal, chronic hepatitis B active stage, active tuberculosis, syphilis outbreak and AIDS.
- (3) Patients with pre-existing severe heart disease, including: congestive heart failure, uncontrollable high-risk arrhythmia, unstable angina, myocardial infarction, severe valvular heart disease, and intractable hypertension.
- (4) Those with neurological or psychiatric diseases or mental disorders that are not easy to control, poor compliance, unable to cooperate with and describe treatment responses, uncontrolled primary brain tumors or central

nervous system metastases, and those with obvious cranial hypertension signs or neuropsychiatric symptoms.

- (5) with malignant serous effusion.
- (6) History of severe enteritis and cystitis, bleeding, intestinal perforation, rectovaginal fistula, rectoval bladder fistula, etc.
- (7) Those who have participated in other clinical trials.
- (8) Other situations in which the investigator believes that the subject is not suitable to participate in this experiment.

2.3 Exit criteria:

- (1) The subject asked to withdraw from the study.
- (2) An irreversible accident occurs.
- (3) Unable to effectively follow up with participants.
- (4) The investigator considers it necessary for the subject to abort the study from a medical point of view.
- (5) Other unforeseen circumstances.

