2.4 Termination of study criteria

- (1) The patient's condition is aggravated.
- (2) Occurrence of serious adverse events.
- (3) Poor patient compliance.

3. Duration of the study

November 2022 to November 2024

4. Research interventions

This study was non-interventional.

5. Study steps and related checks

Before treatment: clear cervical pathology is required to confirm cervical cancer, complete imaging data, hematological data, laboratory test results

and comprehensive medical history.

Treatment period: Complete standard treatment of cervical cancer (concurrent chemoradiotherapy).

Follow-up period: Regular review at 4, 12 and 24 weeks after the end of treatment

6. Use and preservation of biological samples

Cervical tumor tissue was taken twice and made into wax blocks before treatment and during treatment (before the start of the first post-loading treatment); Clinically observe tumor retraction and monitor efficacy.

5ml of peripheral blood was drawn 5 times, respectively, before treatment, during treatment (before the start of the first after-loading treatment), 4 weeks, 12 weeks and 24 weeks after treatment, and serum and white blood cells were retained after treatment; Tested at Nanjing Shihe Medical Laboratory [name]

7. Evaluation indicators/study endpoints

The main endpoint indicators: the expression level and expression status of MRD and plasma HPV before, during, and 4, 12 and 24 weeks after treatment, the relationship between the expression level of MRD and plasma HPV expression status and the efficacy of concurrent chemoradiotherapy for cervical cancer, and the risk of recurrence after concurrent chemoradiotherapy for cervical cancer was predicted.

Secondary endpoints: decision on whether to give adjuvant chemotherapy after the end of concurrent chemoradiotherapy for cervical cancer by the expression level of MRD and the expression status of plasma HPV, as well as the timing of chemotherapy and the benefit of chemotherapy

8. Visiting arrangements and data collection during the study

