From November 01, 2022 to November 31, 2024, 30 patients with newly treated cervical cancer admitted to Guizhou Provincial People's Hospital were included, 30 cervical cancer tissue samples were collected before treatment and during treatment (before the start of the first afterload), and 5ml of peripheral blood of cervical cancer patients was collected before, during treatment (before the start of the first afterload), and 4 weeks, 12 weeks and 24 weeks after the end of treatment to detect MRD expression levels. The relationship between the expression level of MRD and the expression status of HPV in plasma and the efficacy of cervical cancer treatment was analyzed.

Thirty cases of cervical cancer were treated with concurrent chemoradiotherapy, and the efficacy was evaluated 4 weeks after the end of chemoradiotherapy, and the value of MRD expression level and plasma HPV expression status for clinically guided adjuvant chemotherapy and adjuvant chemotherapy time node and clinical benefit were evaluated.

MRD and plasma HPV tests were performed 4 weeks, 12 weeks and 24 weeks after the end of concurrent chemoradiotherapy in 30 cases of cervical cancer to understand the risk of recurrence and predict prognosis. The expression level of MRD and the expression status of HPV in plasma and the clinical value of imaging results in predicting recurrence risk were compared.

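### The stated study duration ends with the inclusion window, leaving no room for treatment and the 4-, 12- and 24-week samples of patients included late

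*Protocol*

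**What the plan says.** The protocol gives these dates and time points:

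- **B.2 (study population):** patients "diagnosed with initial visit to Guizhou Provincial People's Hospital from November 2022 to November 2024 were collected".
- **B.3 (duration of the study):** "November 2022 to November 2024", with nothing added.
- **B.8 (visits and data collection):** "From November 01, 2022 to November 31, 2024, 30 patients with newly treated cervical cancer". This is the same span with days attached, and its end date does not exist.
- **B.5 (study steps):** after treatment, "Follow-up period: Regular review at 4, 12 and 24 weeks after the end of treatment".
- **B.7 (endpoints):** the main endpoint includes the level and status of "MRD and plasma HPV before, during, and 4, 12 and 24 weeks after treatment", related to efficacy and to recurrence risk.
- **B.8 again:** "MRD and plasma HPV tests were performed 4 weeks, 12 weeks and 24 weeks after the end of concurrent chemoradiotherapy in 30 cases".
- **Title page:** "Project Year: 2024/01 – 2026/12", and a version date of 22 May 2023.

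The protocol does not state how long chemoradiotherapy lasts. It does not say how the project period relates to the dates in B.2, B.3 and B.8.

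**The concern.** A study that enrols up to its last day cannot also observe its last patients for a treatment course plus 24 weeks. B.2 and B.3 taken together describe such a study. The samples concerned are main endpoint time points, and B.8 uses the post-treatment tests to judge recurrence risk and prognosis. If someone closed the study on the B.3 date, the missing samples would fall on the patients included last, with week 24 lost first. With about 30 patients, a handful of missing week-24 values would matter to any analysis of recurrence.

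**Working it through.** **The plan's own figure.** B.3 states a duration and shows no calculation behind it. B.2 and B.3 give months only; B.8 supplies the days. I take 1 November 2022 as the start and read the impossible end date as 30 November 2024, which is also the latest day that B.2 and B.3 allow. Counting both ends, the window is 761 days. Time between the last permitted inclusion and the end of study in B.3: 0 days.

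**Time needed after the last inclusion.** Treatment length plus 24 weeks (168 days). Treatment length is not in the protocol, so I use 0, 6 and 8 weeks as assumptions; 0 is a lower bound, not a realistic value.

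**Latest end of treatment that keeps each sample inside B.3** (30 November 2024 minus the interval; no assumption about treatment length is needed):

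| Sample | Days after treatment | Treatment must end by |
|---|---|---|
| Week 4 | 28 | 2 November 2024 |
| Week 12 | 84 | 7 September 2024 |
| Week 24 | 168 | 15 June 2024 |

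**Latest start of treatment for week 24.** With 6 weeks of treatment: 42 + 168 = 210 days before 30 November 2024, which is 4 May 2024. With 8 weeks: 56 + 168 = 224 days, which is 20 April 2024. Any delay between first visit and treatment moves the latest inclusion earlier still.

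**Patients affected at week 24.** The protocol gives no accrual pattern, so only a range is possible.

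- All 30 included early enough: 0.
- Uniform accrual over the 761 days, treatment starting at inclusion:
  - 0 weeks of treatment: 30 × 168/761 = 6.6
  - 6 weeks: 30 × 210/761 = 8.3
  - 8 weeks: 30 × 224/761 = 8.8

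That is about 7 to 9 of 30 under uniform accrual, and 0 to about 9 overall.

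**End of study that would suffice.** If enrolment runs to 30 November 2024, the last week-24 sample falls on 17 May 2025 with no treatment time counted (+168 days), 28 June 2025 with 6 weeks of treatment (+210 days) and 12 July 2025 with 8 weeks (+224 days). The last of these is 537 days before 31 December 2026, the end of the title-page project period.

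**The case against.** The best case for the protocol is that B.3 is loosely headed and means the enrolment period. Nothing says that sampling stops in November 2024. Inclusion criterion (3) expects patients to complete all follow-up, and B.8 reports the three post-treatment tests for 30 cases. With a fixed target of about 30, inclusion could also finish well before the window closes. All this stands as evidence of intent. But it shows that B.3, which is headed and worded as the duration of the study, disagrees with the schedule; it does not make B.3 correct.

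The opening sentence of B.8 can also be read as dating inclusion, tissue collection and all five blood draws together. On that reading B.3 is consistent with B.8, and the inclusion window in B.2 runs too late. The document does not settle which date should move, so the fix has to leave both routes open.

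Four stronger readings are tempting, and the protocol does not support them:

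- **That no patient has follow-up time.** This is true only after the last permitted inclusion. Anyone finishing treatment by 15 June 2024 can give all samples inside B.3.
- **That samples will be lost.** Loss depends on B.3 being enforced and on late accrual. The document shows neither.
- **That the title page contradicts the study dates.** The project period starts 14 months after inclusion opens, but it is an administrative entry that is not called an enrolment or study period, and it may legitimately differ. Its relation to the other dates is merely unexplained.
- **That early patients were included retrospectively.** Inclusion opens on 1 November 2022, 202 days before version 1.0, in a document that says "This is a prospective, observational, single-center study". A version date does not show how earlier patients were enrolled, so no sensitivity analysis is warranted on this evidence.

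**Conclusion.** The point holds. The duration in B.3 is wrong as written, because it equals the inclusion window in B.2 while the main endpoint requires observation to 24 weeks after treatment. The cut-off dates of 15 June, 7 September and 2 November 2024 rest only on reading the end of B.3 as 30 November 2024. The number of patients affected is not determinable from the document. The figure of about 7 to 9 of 30 is conditional on uniform accrual to the last day, treatment starting at inclusion and an assumed treatment length of 0 to 8 weeks; with early accrual it is zero. This is a firm contradiction of dates touching main endpoint time points, not a demonstrated loss of data. It should be corrected, and the correction is simple.

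**What to change.** 1. State the end of enrolment and the end of study as separate dates, and use them consistently in B.2, B.3 and B.8. Either set the end of study at least the treatment course plus 24 weeks after the last inclusion (about mid-2025 if enrolment runs to 30 November 2024, within the December 2026 project end), or keep the November 2024 end and state an earlier close of enrolment.
2. Correct the non-existent 31 November in B.8 at the same time.
3. As a side note, add a sentence saying how the 2024/01 to 2026/12 project period and the 22 May 2023 version date relate to the November 2022 start.

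The cost is a few date corrections. With a later end of study, enrolment, visits and samples stay as they are, and the only downside is a later stated end. With an earlier close of enrolment, the investigator has less time to reach 30 patients.

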2.4 Termination of study criteria

- (1) The patient's condition is aggravated.
- (2) Occurrence of serious adverse events.
- (3) Poor patient compliance.

3. Duration of the study

November 2022 to November 2024

4. Research interventions

This study was non-interventional.

5. Study steps and related checks

Before treatment: clear cervical pathology is required to confirm cervical cancer, complete imaging data, hematological data, laboratory test results

and comprehensive medical history.

Treatment period: Complete standard treatment of cervical cancer (concurrent chemoradiotherapy).

Follow-up period: Regular review at 4, 12 and 24 weeks after the end of treatment

6. Use and preservation of biological samples

Cervical tumor tissue was taken twice and made into wax blocks before treatment and during treatment (before the start of the first post-loading treatment); Clinically observe tumor retraction and monitor efficacy.

5ml of peripheral blood was drawn 5 times, respectively, before treatment, during treatment (before the start of the first after-loading treatment), 4 weeks, 12 weeks and 24 weeks after treatment, and serum and white blood cells were retained after treatment; Tested at Nanjing Shihe Medical Laboratory [name]

7. Evaluation indicators/study endpoints

The main endpoint indicators: the expression level and expression status of MRD and plasma HPV before, during, and 4, 12 and 24 weeks after treatment, the relationship between the expression level of MRD and plasma HPV expression status and the efficacy of concurrent chemoradiotherapy for cervical cancer, and the risk of recurrence after concurrent chemoradiotherapy for cervical cancer was predicted.

Secondary endpoints: decision on whether to give adjuvant chemotherapy after the end of concurrent chemoradiotherapy for cervical cancer by the expression level of MRD and the expression status of plasma HPV, as well as the timing of chemotherapy and the benefit of chemotherapy

8. Visiting arrangements and data collection during the study

From November 01, 2022 to November 31, 2024, 30 patients with newly treated cervical cancer admitted to Guizhou Provincial People's Hospital were included, 30 cervical cancer tissue samples were collected before treatment and during treatment (before the start of the first afterload), and 5ml of peripheral blood of cervical cancer patients was collected before, during treatment (before the start of the first afterload), and 4 weeks, 12 weeks and 24 weeks after the end of treatment to detect MRD expression levels. The relationship between the expression level of MRD and the expression status of HPV in plasma and the efficacy of cervical cancer treatment was analyzed.

Thirty cases of cervical cancer were treated with concurrent chemoradiotherapy, and the efficacy was evaluated 4 weeks after the end of chemoradiotherapy, and the value of MRD expression level and plasma HPV expression status for clinically guided adjuvant chemotherapy and adjuvant chemotherapy time node and clinical benefit were evaluated.

MRD and plasma HPV tests were performed 4 weeks, 12 weeks and 24 weeks after the end of concurrent chemoradiotherapy in 30 cases of cervical cancer to understand the risk of recurrence and predict prognosis. The expression level of MRD and the expression status of HPV in plasma and the clinical value of imaging results in predicting recurrence risk were compared.

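### Section 2.4(3) lets undefined poor compliance end an enrolled patient's participation in a non-interventional cohort, so post-treatment markers and outcomes may never be collected

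*Protocol*

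**What the plan says.** Section 1 (study design) states: "This is a prospective, observational, single-center study". Section 4 (research interventions) adds: "This study was non-interventional". Section 2.4 then gives three grounds for termination: worsening of the patient's condition, a serious adverse event, and "Poor patient compliance". Its heading speaks of terminating the study, but each item describes a single patient, so it reads as a participant-level rule. The protocol does not confirm this.

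Two neighbouring rules cover nearby ground. Exclusion criterion 2.2(4) already keeps out patients with "poor compliance, unable to cooperate with and describe treatment responses". Exit criterion 2.3(3) covers loss to follow-up: "Unable to effectively follow up with participants". Exit criterion 2.3(1) covers patients who ask to leave.

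Sections 5 and 6 give completion of standard concurrent chemoradiotherapy as the step for the treatment period. They plan five blood draws (one before treatment, one during, three after) and post-treatment reviews at weeks 4, 12 and 24. Section 8 places the efficacy evaluation at week 4 and describes the post-treatment marker tests as done in all 30 cases.

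The protocol does not say what a patient must comply with, or what degree of non-compliance triggers the rule. It does not say whether outcome follow-up continues afterwards or whether the patient is replaced.

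**The concern.** A study that assigns no treatment has none to withdraw. Ending participation therefore means ending observation, and it happens after entry, before the main endpoint data are complete. The main endpoint links MRD and plasma HPV, measured up to week 24, to the efficacy of chemoradiotherapy and the risk of recurrence.

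A patient terminated during treatment can lose three of the five blood draws, the efficacy assessment and the recurrence status. If poor compliers respond or recur at the same rate as others, the study loses only numbers and events. If they differ, the remaining patients are a selected group and the marker–outcome results may be biased. With about 30 patients and probably only a handful of failures, losing even one or two matters.

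A later analysis plan can define who is analysed, but it cannot recover blood that was never drawn or recurrence status that was never sought. Who stays under observation is a protocol rule, and this protocol states one.

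**Working it through.** **1. The plan's own figure.** The only computed figure is the sample size of about 30 in the experimental group (section 2: α 0.05, power 0.8, m 0.5). It cannot be reproduced, because δ and σ are not given. The point does not depend on it. No dropout allowance is stated.

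**2. Where the rule can act.**

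| Situation | Rule that covers it |
|---|---|
| Poor compliance recognised at entry | 2.2(4) |
| Patient asks to leave | 2.3(1) |
| Patient cannot be followed | 2.3(3) |
| Enrolled, still reachable, has not asked to leave, judged non-compliant | 2.4(3) only |

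The last row is what 2.4(3) adds to these rules. It consists of patients whose outcome could still be obtained.

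**3. Does the meaning of compliance matter?** Three readings are open: treatment, visits, or blood and tissue sampling. The separate loss-to-follow-up rule and the completion step in section 5 make treatment a likely reading. The absence of any assigned treatment points towards study procedures. Under each reading, follow-up can end while outcomes are still obtainable, so the defect does not depend on which is right.

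**4. Illustration of events lost.** The protocol gives no failure rates and no rate of non-compliance, so every rate here is an assumption. Let k of 30 patients be terminated with failure risk r, and let the others have risk 0.18.

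Failures in all 30 = (30 − k) × 0.18 + k × r. Share lost = k × r ÷ that total.

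| k | r | Failures in all 30 | Rate in all 30 | Share lost | Rate in those kept |
|---|---|---|---|---|---|
| 2 | 0.40 | 5.04 + 0.80 = 5.84 | 19.5% | 0.80/5.84 = 14% | 18% |
| 6 | 0.60 | 4.32 + 3.60 = 7.92 | 26.4% | 3.60/7.92 = 45% | 18% |
| 2 | 0.18 (no relation) | 5.04 + 0.36 = 5.40 | 18% | 0.36/5.40 = 7% | 18% |
| 6 | 0.18 (no relation) | 4.32 + 1.08 = 5.40 | 18% | 1.08/5.40 = 20% | 18% |

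The 18% in the last column is simply the assumed input. It is not a finding.

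**5. Same check with other assumed rates.** Take 20% recurrence in compliant patients and 5–30% of the cohort terminated. The share of recurrences lost is 10–46% if non-compliant patients recur at 40%, 14–56% at 60%, and 5–30% if they also recur at 20%. One case worked through: with 10% terminated and 40% recurrence among them, the full cohort expects 27 × 0.2 + 3 × 0.4 = 6.6 recurrences. The 27 retained patients show 5.4, so 1.2/6.6 = 18% are lost.

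**6. Precision.** Suppose the 30 patients came from a two-sided comparison of two means with m as the ratio of control to experimental patients (an assumption). Then δ/σ = √(3 × (1.960 + 0.842)² / 30) ≈ 0.886. Power at n patients is Φ(0.886 × √(n/3) − 1.960), if both groups shrink in proportion. That gives 80% at 30, 76% at 27, 71% at 24 and 65% at 21.

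**The case against.** The strongest case against runs as follows.

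- **Meaning of compliance.** A reader might infer that the cohort becomes one of treatment completers. The protocol does not support that as a statement of fact: it never says what patients must comply with, and a non-interventional study could mean only its own draws, biopsies and visits. This part of the objection stands.
- **Removal from the analysis.** A reader might also infer that terminated patients are dropped from the analysis. Section 2.4 does not say so. Analysis sets, missing time points and completers-only sensitivity analyses are commonly left to the analysis plan. This stands too, and none of them is claimed here as an omission.
- **Direction of bias.** It is tempting to add that the rule would weaken the marker–outcome association. Nothing in the protocol shows this. Restricting to compliant patients might instead remove confounding by treatment received. The direction is open.
- **Size.** The 14–45% range follows entirely from assumed rates, and with no relation between compliance and failure only precision is lost. This stands.
- **Target population.** The title and section 5 concern patients after chemoradiotherapy, so a population that completed treatment would be a legitimate target. If that is the intention, the protocol should state it as a defined population. An undefined compliance rule applied during follow-up does not do that.
- **Priority.** 2.4(1), on worsening of the patient's condition, selects more directly on outcome. That is so, but correcting it would leave 2.4(3) in force.

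What the objection does not remove is a written rule that can end observation of reachable patients before the endpoint data exist.

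**Conclusion.** The point holds in a limited form. Section 2.4(3), followed as written, allows selection after entry in a non-interventional cohort, through an undefined criterion, for patients not already covered by the entry screen, voluntary withdrawal or loss to follow-up.

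The loss of events and precision follows whenever the rule is used and observation stops. Bias follows only if compliance is related to response or recurrence, which is plausible but not stated in the protocol. Its size and direction cannot be derived from the document.

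The conclusion rests on two readings: that 2.4 applies to individual patients, and that terminating participation ends data collection. The protocol states neither outright, and it should settle both. This is worth correcting before further enrolment, with medium confidence.

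**What to change.** 1. Remove item (3) from section 2.4 as a ground for ending study follow-up.
2. State that a missed blood draw or visit makes only that time point missing.
3. State that outcome status (efficacy assessment and recurrence) continues to be collected for every enrolled patient who started chemoradiotherapy and has not withdrawn under 2.3(1).
4. Record the treatment each patient actually received.
5. Say whether section 2.4 applies to single patients or to the whole study.

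If item (3) was also meant to govern clinical care, that is for the investigators to reconcile with section 4. Nothing here changes any treatment rule.

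The cost is one deleted line, two or three added sentences, and some extra effort to obtain outcomes for patients who miss visits. No extra patients or scheduled samples are needed.

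### Scheduled follow-up ends at the visit of the last blood sample, so the week-24 marker has no later recurrence to predict and the week-12 marker has only 12 weeks of outcome

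*Protocol*

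**What the plan says.** - **Follow-up (B.5):** "Follow-up period: Regular review at 4, 12 and 24 weeks after the end of treatment". No later review, scan or outcome check is scheduled.
- **Blood samples (B.6):** "5ml of peripheral blood was drawn 5 times, respectively, before treatment, during treatment", and then "4 weeks, 12 weeks and 24 weeks after treatment, and serum and white blood cells were retained after treatment". The last sample and the last review share one visit.
- **Main endpoint (B.7):** besides marker levels and their relation to treatment efficacy, it states that "the risk of recurrence after concurrent chemoradiotherapy for cervical cancer was predicted".
- **Use of the post-treatment tests (B.8):** the tests at weeks 4, 12 and 24 are done "in 30 cases of cervical cancer to understand the risk of recurrence and predict prognosis". The markers are also to be compared with imaging as predictors of recurrence.
- **Time frames:** B.3 gives the duration of the study as "November 2022 to November 2024", the same months as patient inclusion in B.2 and B.8. The title page has "Project Year: 2024/01 – 2026/12", with no visit or outcome collection attached to it.
- **Termination (B.2.4):** one criterion is "The patient's condition is aggravated".

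**The concern.** Prediction requires a marker reading first and an outcome afterwards. If outcome observation ends at the visit of the last sample, that sample can show only whether the marker agrees with disease status on the same day. The week-12 sample has a short window in which few recurrences can be expected. The planned comparison of markers with imaging meets the same limit for readings taken at those visits.

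Two other passages make this worse. A study duration equal to the recruitment window leaves late entrants no time to complete even the 24-week schedule. And the termination criterion, read literally, could end observation at recurrence, the very event to be predicted.

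A statistical analysis plan cannot repair this. It can define analyses, but it cannot create outcomes that the protocol does not arrange to collect.

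**Working it through.** **1. Scheduled outcome time (protocol figures only).** Window = week of last review (24, B.5) minus week of sample (B.6).

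- Week 4: 24 − 4 = 20 weeks
- Week 12: 24 − 12 = 12 weeks
- Week 24: 24 − 24 = 0 weeks

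The pre-treatment and mid-treatment samples have more than 24 weeks and are less affected.

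**2. Expected recurrences (illustration).** N = 30 is from the protocol, which gives no recurrence rate. I assume two-year (104-week) recurrence p of 20%, 30% or 40%, measured from the end of treatment at constant hazard. Then S(w) = (1 − p)^(w/104), and the expected events between weeks a and b are 30 × [S(a) − S(b)]. For example, p = 0.3 and weeks 0–24: 30 × (1 − 0.7^(24/104)) = 2.37.

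| Interval | p = 20% | p = 30% | p = 40% |
|---|---|---|---|
| Weeks 0–24 | 1.51 | 2.37 | 3.34 |
| Weeks 4–24 | 1.25 | 1.96 | 2.75 |
| Weeks 12–24 | 0.74 | 1.16 | 1.62 |
| After week 24, as scheduled | 0 | 0 | 0 |
| Weeks 0–104 | 6 | 9 | 12 |
| Weeks 24–104 | 4.49 | 6.63 | 8.66 |

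Under these assumptions, 72% to 75% of two-year recurrences fall after scheduled follow-up (4.49/6 = 75%, 6.63/9 = 74%, 8.66/12 = 72%). If recurrence is concentrated early, with a 24-week risk of 10% to 20%, events by week 24 would be 30 × 0.10 = 3 to 30 × 0.20 = 6. The zero after week 24 does not change.

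**3. Precision.** Exact (Clopper-Pearson) 95% intervals for an observed sensitivity of 67%:

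| Detected / recurrences | 95% interval |
|---|---|
| 2/3 | 9–99% |
| 4/6 | 22–96% |
| 6/9 | 30–93% |
| 8/12 | 35–90% |

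If only recurrences after week 24 are counted, follow-up to week 104 gives the week-24 marker about 4.5 to 8.7 events. The 4/6 and 6/9 rows are then the relevant ones, except that the lowest assumed rate would be less precise than 4/6. The 12-event row applies only when all recurrences since the end of treatment are counted at the highest assumed rate.

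**4. Dates.** B.8 ends inclusion on 31 November 2024, a date that does not exist, so I use 30 November. The window from 1 November 2022 is then 760 days. Treatment length is assumed to be 5, 7 or 10 weeks, starting at enrolment.

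| Quantity | 5 weeks | 7 weeks | 10 weeks |
|---|---|---|---|
| Enrolment to week 24 | 29 weeks | 31 weeks | 34 weeks |
| Week 24 for a patient starting 30 Nov 2024 | 21 Jun 2025 | 5 Jul 2025 | 26 Jul 2025 |
| Latest start that reaches week 24 by 30 Nov 2024 | 11 May 2024 | 27 Apr 2024 | 6 Apr 2024 |
| Share of window after that date | 203/760 = 26.7% | 217/760 = 28.6% | 238/760 = 31.3% |
| Of 30 patients at even accrual | 8.0 | 8.6 | 9.4 |
| Last patient's week 24 to 31 Dec 2026 | 79.7 weeks | 77.7 weeks | 74.7 weeks |

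Adding 24 weeks to the last row puts even the last patient at about 99 to 104 weeks after treatment by the end of the project period.

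**The case against.** The strongest reply is that the protocol never says outcome collection stops at week 24. The title names prognosis, the project period runs about 25 months beyond the close of recruitment, and B.5 could be read as listing only the sampling visits. This stands in part: whether later outcomes are collected is open. But the protocol schedules none, and the one section that states the study duration ends it in November 2024. The conclusion is therefore limited to scheduled follow-up.

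Second, much of the main endpoint is untouched. Marker levels at five time points and their relation to efficacy, assessed at week 4, need no later outcome. The three post-treatment tests could also be read as one series, with week 24 serving partly as surveillance. That is fair: the gap is complete only for week 24 and partial for week 12. Still, B.8 names week 24 among the tests meant to predict.

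Third, the event counts rest on assumed rates, and with 30 patients longer follow-up still leaves wide intervals. Both points stand. The counts show scale; the conclusion does not depend on them.

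Fourth, the termination wording is undefined and may be a matter of translation, so it supports only a request to clarify. Which recurrences to relate to which reading could also be set out in the statistical analysis plan. Arranging to collect the outcomes could not.

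**Conclusion.** The concern holds. Within scheduled follow-up the week-24 marker has no later outcome, the week-12 marker has 12 weeks and the week-4 marker has 20; this rests on the protocol's own visit schedule. As scheduled, the study can report agreement between the week-24 marker and disease status that day, but not prediction of recurrence from it, and week-12 prediction is only weakly answerable.

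On the assumed rates, 0.7 to 1.6 recurrences would inform week 12 as scheduled, and 4.5 to 8.7 would become available to week 24 with follow-up to two years. With even accrual and 5 to 10 weeks of treatment, 8 to 9 of 30 patients could not complete week 24 within the stated duration.

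This should be fixed, because it decides what the study can say about recurrence. Confidence is moderate, since the conflicting time frames leave open whether later outcomes are in fact collected.

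**What to change.** - Keep the blood sampling schedule. Add outcome-only follow-up, by records or telephone, for recurrence and death to one common cut-off for all patients within the project period ending 2026/12.
- Reconcile the study duration in B.3 with that project period and with the recruitment window.
- Reconcile the termination criterion on worsening condition (B.2.4) with the need to record recurrence.
- Relate each post-treatment marker or imaging reading only to recurrences diagnosed after that visit, in patients recurrence-free at it. Report same-visit agreement as concurrent detection. The detail may sit in the statistical analysis plan.

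The cost is an amendment to the follow-up, duration and termination sections and modest record or telephone work for 30 patients, with no extra samples or scans. If ethics approval or consent covers only the shorter period, it would need extending. The final recurrence report would come later, and it should state that precision remains low.
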